1. SYNOPSIS

COMPOUND: OraVerse®

STUDY NO.: PHENLL07113

Title	Actual conditions of use of OraVerse® in patients among resident dentists throughout Germany
Location	Germany
Objectives	To investigate the conditions of use of OraVerse® after local anesthetic procedure in daily routine practice. The primary outcome will be the incidence of patients who "comply"/"not comply" with the recommendations in the SmPC regarding the following points: • patient age, • classification of body weight • type of dental intervention, • local anesthetic used (product and dose), • dose of OraVerse® used
Population	 Inclusion Criteria Patients treated with OraVerse® after treatment with a local anesthetic containing a vasoconstrictor (such as epinephrine) by dentists within the last 3 months before contract signing Expected number of patients: 526 (500 evaluable) Sample Size: 500 treated (evaluable) patients assuming a 5% non-evaluable rate. Expected number of sites: ca. 100 To gather a nationwide number of resident dentists
Population	 Inclusion Criteria Patients treated with OraVerse® after local anesthetic procedure by dentists within the last 3 months before contract signing Expected number of patients: 526 (500 evaluable) Sample Size: 500 treated (evaluable) patients assuming a 5% non-evaluable rate. Expected number of sites: ca. 100 To gather a nationwide number of resident dentists

Recruitment modalities

Retrospective cross-sectional drug utilisation survey among resident dentists throughout Germany

- Eligible patients:
 - All patients normally treated with OraVerse® after local anesthetic procedure by dentists within the last 3 months before contract signing
- Participating dentists:
 - must be practicing dentists working in private practices,
 - must be dentists performing routine dental interventions using local anesthetic procedure,
 - must have used OraVerse® in the 3 previous months.

Main evaluation criteria

• Primary outcomes:

The outcomes of interest will be the conditions of use of treatment. The primary outcomes will be the incidence of patients who "comply"/"not comply" with the recommendations in the SmPC regarding the following points:

- patient age,
- classification of body weight
- type of dental intervention,
- local anesthetic used (product and dose),
- dose of OraVerse[®] used

Main data collected

Dentists will be asked

- to indicate total number of patients normally treated with OraVerse® within the previous 3 months,
- to record retrospective data coming from the charts of eligible patients (latest consecutive administrations of OraVerse® within the last 3 months up to a maximum of 6 patients) including patient age, classification of body weight, type of dental intervention, name and dose of the product for anaesthetic procedure, dose of OraVerse®

Information will be obtained anonymously directly from patients files by dentists retrospectively.

Statistical methodology

Descriptive statistics for all collected and derived data will be provided. For continuous data number of patients, mean, standard deviation, median, min, max, quartiles and appropriate other percentiles will be provided. For categorical data frequencies and percentages will be presented. For estimated parameters suitable 95 % confidence intervals will be provided.

Statistical power and sample size justification:

With a sample size of 500 patients the following statistical precision for the estimated proportion of patients who 'not comply'/'comply' with the doses and indications recommended in the SmPC can be reached: Assuming rates of not adherence/adherence to labelling of 3%/97% or 4%/96% or 5%/95%, the 2-sided 95% confidence intervals will be [1.5%; 4.5%]/[95.5%; 98.5%] or [2.3%; 5.7%]/[94.3%; 97.7%] or [3.1%; 6.9%]/[93.1%; 96.9%].

In general: when the sample size is 500, a two-sided 95.0% confidence interval for a single proportion using the large sample normal approximation will extend 0.015 or 0.017 or 0.019 from the observed proportion for an expected proportion of 0.030 (or 0.97) or 0.04 (or 0.96) or 0.05 (or 0.95).

Timelines

Protocol planned date: February 2014

Database lock planned date: 31 July 2014

Duration of retrospective survey/data collection: planned May - June 2014

Estimated Report date: January 2015

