5. STUDY DESIGN

5.1 Description of the study design

This drug utilization survey is described in the RISK MANAGEMENT PLAN (RMP) of OraVerse® and was requested during the European approval procedure. It will provide further information about the conditions of use of OraVerse® in routine clinical practice (i.e. patient age, type of dental intervention, local anesthetic used (product and dose) and dose of OraVerse®) used in patients normally treated with OraVerse® after local anesthetic procedure by dentists. It also provides information about use for orofacial procedures other than routine dental procedures, use in children < 6 years or use in patients undergoing complex dental procedures, i.e. for indications different from those described in the SmPC.

The only way to monitor the use of the product will be to collect information directly from dentists. In order to limit intervention bias, a retrospective (retrolective) design will be used to evaluate patients already treated with OraVerse[®].

As OraVerse® is planned to be used by dentists in the frame of dental interventions and will not be reimbursed, it will not be recorded in any national databases/registers in the countries where it will be used. So, the collection of information on patients profile and characteristics of dental intervention will need to be made at dentists' level.

Data documentation will happen after signing the contract:

In order to limit intervention bias, a retrospective design will be used to collect data of the latest
consecutive administrations of OraVerse® within the last 3 months up to a maximum of 6 patients
after signing the contract.

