6.2 Eligibility criteria

6.2.1 Inclusion criteria

 Patients treated with OraVerse® after local anesthetic procedure (with a local anesthetic containing a vasoconstrictor) by dentists within the last 3 months before contract signing

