6.3 Modalities of recruitment

6.3.1 Dentist selection

To gather a nationwide number of resident dentists, the expected number of sites is ca. 100 of practicing dentists working in private practices throughout Germany.

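### The synopsis admits only dentists who do routine work, so private practices doing solely non-routine work, part of the use Section 5.1 promises to describe, cannot enter the survey

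*Protocol*

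**What the plan says.** The synopsis of the protocol, under recruitment modalities, sets three conditions for a participating dentist. The first concerns setting: dentists "must be practicing dentists working in private practices". The second concerns activity: they "must be dentists performing routine dental interventions using local anesthetic procedure". The third is use of OraVerse in the preceding three months.

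Section 6.3.1 describes site selection again and keeps only the setting: "the expected number of sites is ca. 100 of practicing dentists working in private practices throughout Germany". The activity condition does not appear there.

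Section 5.1 states what the survey is meant to show beyond ordinary use: "use for orofacial procedures other than routine dental procedures, use in children < 6 years or use in patients undergoing complex dental procedures". It treats these as uses outside the SmPC. Section 11.2.1 makes the extent of use for other indications part of the primary outcome, under type of dental intervention.

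At patient level there is no restriction by procedure. Section 6.2.1 includes "Patients treated with OraVerse® after local anesthetic procedure (with a local anesthetic containing a vasoconstrictor) by dentists within the last 3 months before contract signing", and the synopsis and Section 5.1 take the most recent consecutive administrations, at most six per dentist.

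**The concern.** The activity condition selects sites on the characteristic that one primary variable measures. Type of dental intervention is judged by whether the procedure was a routine dental one in the sense of the label. A dentist enters the survey only if he or she does routine work. A private practice confined to surgical or other non-routine procedures has no chance of selection, even if it uses OraVerse and even though its dentist is a resident dentist of the kind named in the title.

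The protocol gives no reason for the condition. Section 5.1 explains only why the data must come from dentists: the product is not reimbursed and is recorded in no register. That reason applies equally to practices without routine work.

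At stake is the procedure-type non-compliance rate in a survey that, according to Section 3.2, was requested during the European approval procedure and is to examine use according to labelling. A larger sample would not repair a gap in coverage, and the confidence intervals in Section 11.4 reflect sampling error only. The gap could not be examined afterwards either, because Section 13.3 provides for CRFs without site number and practice type is not among the data items listed.

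**Working it through.** **1. The plan's own precision.** Inputs from Section 11.4: n = 500, expected non-adherence p of 3%, 4% or 5%, two-sided 95% interval by normal approximation. Half-width = 1.96 × √(p(1 − p)/500).

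- p = 3%: 0.0150, interval 1.5% to 4.5%
- p = 4%: 0.0172, interval 2.3% to 5.7%
- p = 5%: 0.0191, interval 3.1% to 6.9%

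These agree with the protocol. They do not depend on the site criteria, so they neither support nor refute the point. They serve below only as a yardstick.

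**2. Who is excluded.** The activity condition does not contain the word only. A dentist who does routine work and also complex work qualifies. The dentists who fail it are those who do no routine interventions under local anaesthesia.

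**3. Direction.** OraVerse is given after local anaesthesia. In an excluded practice, every administration therefore follows a non-routine intervention. If routine has the same meaning in the site criterion as in the indication described in Section 3.1, each such administration counts as not complying on procedure type. The non-compliance rate in the excluded practices is then 100% by construction, whereas the rate p among admitted practices is lower.

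Let s be the share of the survey's patients who would come from such practices if they were admitted. Then:

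- rate with these practices included = (1 − s) × p + s × 1
- shortfall caused by the exclusion = s × (1 − p)

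The shortfall is never negative. It is zero when s = 0.

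**4. Size.** The documents give no value for s. The values of s below are assumptions. The values of p are borrowed from Section 11.4, where they refer to doses and indications together and not to procedure type alone.

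| s (assumed) | p = 3% | p = 4% | p = 5% |
|---|---|---|---|
| 0% | 3.00% | 4.00% | 5.00% |
| 1% | 3.97% | 4.96% | 5.95% |
| 2% | 4.94% | 5.92% | 6.90% |
| 5% | 7.85% | 8.80% | 9.75% |

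Example: 0.98 × 4% + 0.02 × 100% = 5.92%.

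The shortfall equals the planned half-width when s = half-width/(1 − p): 0.015/0.97 = 1.5%, 0.017/0.96 = 1.8% and 0.019/0.95 = 2.0%. At about 100 sites contributing similar numbers, that is roughly two sites. This shows only that a small share would matter. It is not evidence that such a share exists.

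**The case against.** The strongest reply is that the condition is a floor. Private oral-surgery or paediatric practices that do some routine work are already eligible. Patients are taken consecutively whatever the procedure, and the type of intervention is recorded for each. Section 5.1 can therefore be met within the sampled practices, and nothing in the protocol suggests that practices with no routine work account for material use. The analyses are also declared exploratory in Section 11.3. All of this stands: the fault is incomplete coverage, and it may be empty in practice. What remains is that the condition serves no stated purpose and that any effect on this variable goes in one direction.

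A reader might go further and infer that the survey samples routine interventions only, or that overall compliance is overstated because hospital and university departments are shut out. The documents do not support either reading. The first ignores the patient criteria. As to the second, the title and objectives aim at resident dentists and daily routine practice, and a private-practice frame largely fits that aim. The share of use in hospitals and the non-compliance rate there are not given, so both direction and size would be assumed. Nor is any effect shown on compliance with age, body weight or dose.

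Adding hospital departments to the same 100 or so sites would also not be a clean remedy. Without weights, their share of the pooled rate would be arbitrary, and the target population would have changed.

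**Conclusion.** The point holds in a limited form. The activity condition in the synopsis excludes a group of resident dentists whose use, if there is any, would be entirely non-compliant on procedure type. It can therefore only lower the estimated procedure-type non-compliance rate. The direction rests on one assumption, that routine means the same in the site criterion and in the labelled indication. The size cannot be estimated from the documents and is zero if such practices do not use OraVerse.

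Separately, Section 5.1 announces information on non-routine and complex use without saying that it comes from private practices alone. That is a matter of stating the scope. It does not show that the compliance estimate for the declared target is wrong.

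**What to change.** - In the synopsis, delete the condition that dentists "must be dentists performing routine dental interventions using local anesthetic procedure". Any resident dentist in private practice who used OraVerse in the preceding three months then qualifies. This also brings the synopsis into line with Section 6.3.1.
- Add a practice-type tick box to each CRF. A box on the overview page cannot be relied on, because CRFs carry no site number and the protocol provides no identifier linking the two. Broad categories would preserve anonymity.
- Keep the private-practice frame. State in Section 5.1 and in the objective that results on non-routine and complex use apply to private practices only and do not describe hospital or university settings.

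The cost is protocol wording and one CRF item, with no additional sites or patients. The downside is a slightly more mixed set of sites and a narrower stated claim.

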2. LIST OF ABBREVIATIONS

CRF Case Report Form

CRO Contract Research Organization

GEP Good Epidemiological Practices

IEC Independent Ethics Committee

IRB Institutional Review Board

NA Not Applicable

NIS Non Interventional Study

RMP Risk Management Plan

SmPC Summary of Product Characteristics

3. INTRODUCTION AND RATIONALE

3.1 Background

Phentolamine mesylate, the active ingredient of OraVerse[®], a pharmaceutical product marketed since the 1950s, is a competitive non-selective $\alpha 1$ and $\alpha 2$ -adrenergic receptor blocker of relatively short duration. When applied to vascular smooth muscle, it produces an alpha-adrenergic block resulting in vasodilatation.

The first indication for phentolamine mesylate was for the control of hypertensive emergencies, most notably due to pheochromocytoma, where it is administered by intravenous (IV) or intramuscular (IM) injection at doses ranging from 3 to 5 mg.

The vasodilatation properties of phentolamine led to its development as OraVerse® for the reversal of soft tissue anaesthesia (lip and tongue): Prolonged soft tissue anesthesia is an unwanted side effect of local dental anesthesia, especially in routine, restorative or hygienic dental procedures. The local anesthetic remains in and around the nerves in the lips, cheek and tongue, causing the unwanted side effect of lingering numbness. This numbness can last up to five hours following treatment^{1,2}. During this period patients have difficulties in speaking, eating and drinking, preventing patients from returning to their daily activities. Prolonged numbness, especially in children, can result in injury due to accidental biting of the lip and/or tongue³.

OraVerse® has achieved the Marketing Authorisation in 2012 in Germany for the reversal of soft tissue anesthesia (lip and tongue) and the associated functional deficits, resulting from an intraoral submucosal injection of a local anesthetic containing a catecholamine vasoconstrictor (such as epinephrine) after routine dental procedure such as teeth cleaning, scaling and planning, cavity filing, crowns. Randomized, controlled studies4 proved the efficacy and safety of OraVerse® in this indication. A reduction was shown of the median time for full sensation to return to the lower lips by 85 minutes (55%) and to the upper lips by 83 minutes (62%) – or by more than half the usual time⁴.

OraVerse® is intended to be used at doses ranging from 200 to 800 micrograms in adults administered by intraoral submucosal injection. The OraVerse® cartridge must be used in an appropriate CE certified syringe system that will permit aspiration. OraVerse® is indicated in adults and children 6 years of age and older and weighing at least 15 kg. It is contraindicated in patients who are hypersensitive to the active substance or to any of the excipients.

Local reactions such as post-procedural pain (6%) and injection site pain (5.3%) were identified risk with OraVerse® during the clinical trials; other common adverse drug reactions include headache, tachycardia, bradycardia, increased blood pressure/hypertension and oral pain. The majority of adverse reactions were mild and resolved within 24 hours.

The efficacy of OraVerse® was evaluated in double-blinded, randomized, multicentre, controlled studies in patients undergoing dental restorative or periodontal maintenance procedures. The control group consisted

of patients receiving a sham injection. OraVerse® reduced the median time to recovery of normal sensation in the lower lip by 85 minutes (55%) compared to control (p < 0.0001). The median time to recovery of normal lip sensation in the upper lip was reduced by 83 minutes (62%) compared to control (p < 0.0001). There was a significant reduction (p < 0.0001) in the time to return to normal oral function (speaking, smiling, drinking and lack of drooling) in the OraVerse® group compared to control.

Before administering OraVerse®, the majority of patients included in the clinical studies were treated with local anaesthetic and a vasoconstrictor (eg. epinephrine) at 1:100000 concentration. Limited data have been submitted to support the efficacy of OraVerse® when a local anaesthetic and a vasoconstrictor (eg. epinephrine) at concentration less than 1:100000 is administered.

In clinical studies, paediatric patients between the ages of 3 and 17 years received OraVerse[®]. The median time to normal lip sensation in patients 6 to 11 years of age was reduced by 75 minutes (56 %) compared to control (p < 0.0001).

In clinical studies of OraVerse®, no overall differences in safety or effectiveness were observed between elderly patients and younger patients.

3.2 Rationale

This retrospective drug utilisation survey is described in the RISK MANAGEMENT PLAN (RMP) of OraVerse® and was requested during the European approval procedure. It is planned to investigate the conditions of use of OraVerse® after local anesthetic procedures in daily routine clinical practice, whatever the concentrations of local anesthetics used is and to investigate the use of OraVerse® according to labelling.

4. STUDY OBJECTIVES

Primary objectives:

To investigate the conditions of use of OraVerse® after local anaesthetic procedure in daily routine. The documentation will include the following points:

total number of patients treated with OraVerse® within the previous 3 months

latest consecutive administrations of OraVerse® within the last 3 months up to a maximum of 6 patients before contract signing:

- patient age,
- classification of body weight
- type of dental intervention,
- local anesthetic used (product and dose),
- dose of OraVerse® used

5. STUDY DESIGN

5.1 Description of the study design

This drug utilization survey is described in the RISK MANAGEMENT PLAN (RMP) of OraVerse® and was requested during the European approval procedure. It will provide further information about the conditions of use of OraVerse® in routine clinical practice (i.e. patient age, type of dental intervention, local anesthetic used (product and dose) and dose of OraVerse®) used in patients normally treated with OraVerse® after local anesthetic procedure by dentists. It also provides information about use for orofacial procedures other than routine dental procedures, use in children < 6 years or use in patients undergoing complex dental procedures, i.e. for indications different from those described in the SmPC.

The only way to monitor the use of the product will be to collect information directly from dentists. In order to limit intervention bias, a retrospective (retrolective) design will be used to evaluate patients already treated with OraVerse[®].

As OraVerse® is planned to be used by dentists in the frame of dental interventions and will not be reimbursed, it will not be recorded in any national databases/registers in the countries where it will be used. So, the collection of information on patients profile and characteristics of dental intervention will need to be made at dentists' level.

Data documentation will happen after signing the contract:

In order to limit intervention bias, a retrospective design will be used to collect data of the latest
consecutive administrations of OraVerse® within the last 3 months up to a maximum of 6 patients
after signing the contract.

5.2 Duration of the study (data documentation)

Duration of retrospective survey/data documentation: planned May – June 2014.

5.3 Evaluation criteria

The outcome will be

- patient age,
- classification of body weight,
- type of dental intervention,
- local anesthetic used (product and dose),
- dose of OraVerse® used.

6. STUDY POPULATION AND SELECTION OF PATIENTS

6.1 Sample size

Expected number of patients: ca. 526 (500 evaluable)

It is planned to recruit 500 treated (evaluable) patients assuming a 5 % non-evaluable rate in Germany.

6.2 Eligibility criteria

6.2.1 Inclusion criteria

 Patients treated with OraVerse® after local anesthetic procedure (with a local anesthetic containing a vasoconstrictor) by dentists within the last 3 months before contract signing

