11. STATISTICAL METHODOLOGY

11.1 Analysis population(s)

 Patients treated with OraVerse® after local anaesthetic procedure by dentists within the last 3 months before contract signing

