11.2.1 Primary variables - criteria

The primary outcome will be the incidence of patients who "comply"/"not comply" with the recommendations in the SmPC regarding the following points:

- patient age
 - The extent to which OraVerse® has been used in children <6 years
- type of dental intervention
 - The extent to which OraVerse® has been used for indications other than recommended in the SmPC
- local anesthetic used (product and dose),
- dose of OraVerse[®]
 - The extent to which doses of OraVerse® has been used other than recommended in the SmPC (dose of OraVerse® depends on e.g. patient's age, class of body weight and dose of used local anesthetic)

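### Section 6.2.1 makes a vasoconstrictor-containing anaesthetic an entry condition, which removes one route to label non-compliance from the primary outcome and conflicts with the population in section 11.1

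*Protocol*

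**What the plan says.** The protocol words eligibility in two ways.

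- Restricted: section 6.2.1 takes patients treated "after local anesthetic procedure (with a local anesthetic containing a vasoconstrictor) by dentists within the last 3 months before contract signing". The first Population row of the Synopsis has "after treatment with a local anesthetic containing a vasoconstrictor (such as epinephrine) by dentists within the last 3 months before contract signing".
- Unrestricted: the second Population row and the eligible-patients bullet of the Synopsis have "after local anesthetic procedure by dentists within the last 3 months before contract signing". The analysis population in section 11.1 has "after local anaesthetic procedure by dentists within the last 3 months before contract signing".

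Section 3.1 describes the authorised indication as reversal of soft tissue anaesthesia "resulting from an intraoral submucosal injection of a local anesthetic containing a catecholamine vasoconstrictor (such as epinephrine"), so a catecholamine vasoconstrictor is part of the label.

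Section 11.2.1 sets the endpoint: "The primary outcome will be the incidence of patients who 'comply'/'not comply' with the recommendations in the SmPC regarding the following points". The listed points include "local anesthetic used (product and dose") and, under type of intervention, "The extent to which OraVerse® has been used for indications other than recommended in the SmPC".

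**The concern.** The survey was requested during the European approval procedure to show whether use follows the labelling (section 3.2). A condition of the label should then be something the survey measures. Section 6.2.1 instead applies a version of one label condition before any patient is counted. OraVerse given after an anaesthetic with no vasoconstrictor lies outside the indication and within the scope of the primary outcome, yet 6.2.1 bars it from the sample.

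The protocol does not treat its other label limits this way. The label starts at 6 years and 15 kg (section 3.1). Even so, younger children are admitted so that they can be counted (sections 5.1 and 11.2.1), and a weight class below 15 kg is provided (section 11.2).

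The two wordings also leave sites without a single rule. Dentists receive the protocol (section 8.2) and could apply either one. A dentist who applies 6.2.1 must pass over some uses when documenting the most recent consecutive ones. The CRFs carry no patient or site number and cannot be traced back (section 13.3), and there is no quality control at site level (section 9.2). After collection nobody could add the omitted patients or tell which rule a site had used.

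**Working it through.** **Inputs from the protocol.** 500 evaluable patients; two-sided 95% interval by normal approximation; assumed non-adherence of 3%, 4% or 5% (section 11.4).

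**Inputs that must be assumed.** q is the share of all OraVerse uses that follow a vasoconstrictor-free anaesthetic, all of them non-compliant by the indication in 3.1. The documents give no value, so a range is shown. p is non-compliance among the remaining uses. The 3% to 5% of section 11.4 is borrowed for p, although that section states it for adherence to doses and indications as a whole.

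**Step 1, the plan's own precision.** Half-width = 1.96 × √(p(1 − p)/500).

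- p = 3%: 0.0150, interval 1.5% to 4.5%
- p = 4%: 0.0172, interval 2.3% to 5.7%
- p = 5%: 0.0191, interval 3.1% to 6.9%

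All three agree with section 11.4. The planned number also agrees: 500/0.95 = 526.3, stated as about 526. The precision arithmetic is sound and is not affected by this point.

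**Step 2, effect of full exclusion.** Over all uses the rate is q + (1 − q)p. A sample from which every vasoconstrictor-free use is excluded estimates p. The understatement is q + (1 − q)p − p = q(1 − p), which is never negative.

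| q | Rate over all uses (p = 3%) | Understatement (p = 3%) | Understatement (p = 4%) | Understatement (p = 5%) |
|---|---|---|---|---|
| 0% | 3.00% | 0 | 0 | 0 |
| 1% | 3.97% | 0.97 points | 0.96 points | 0.95 points |
| 2% | 4.94% | 1.94 points | 1.92 points | 1.90 points |
| 5% | 7.85% | 4.85 points | 4.80 points | 4.75 points |

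**Step 3, comparison with the planned precision.** The understatement equals the half-width when q = half-width/(1 − p):

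- p = 3%: 0.0150/0.97 = about 1.5%
- p = 4%: 0.0172/0.96 = about 1.8%
- p = 5%: 0.0191/0.95 = about 2.0%

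**Step 4, what the restriction does not remove.** Section 6.2.1 asks for a vasoconstrictor, whereas 3.1 asks for a catecholamine vasoconstrictor. Use with a non-catecholamine vasoconstrictor, with a low vasoconstrictor concentration, with any dose of anaesthetic or OraVerse, at any age, or for any type of intervention still enters the sample and can be judged against the SmPC.

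**The case against.** The strongest reply is that the effect may be small or absent. The documents do not give q. Section 3.1 describes the product as an alpha-blocker that acts by vasodilatation, which gives some reason to think that use without a vasoconstrictor is uncommon. Sections 3.2 and 5.1 name the uses of interest (any anaesthetic concentration, non-routine orofacial procedures, children under 6, complex procedures). Vasoconstrictor-free anaesthesia is not among them, and all of these uses stay eligible. The analyses are descriptive and exploratory (section 11.3). All of this stands, and it limits the size of the bias. It does not remove the defect: section 11.2.1 counts any use outside the recommended indications, and a survey that excludes this use could not show that q is zero.

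It can also be said that 11.1 is shorthand for patients already admitted under 6.2.1, since section 6.3.2 refers to patients meeting the inclusion criteria, and that the twin Population rows look like an editing remnant. That is possible. The eligible-patients bullet would still differ from 6.2.1, and on this reading the restriction governs the whole survey.

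Three stronger readings are tempting but not supported:

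- A reader might infer that vasoconstrictor-free use can never be recorded, or that the survey would report 3% whatever the truth. That holds only if every site applies 6.2.1. Under the other wording such patients enter, and the recorded product could reveal them.
- A reader might infer that non-compliance in the local anaesthetic domain is driven to zero. Only one route is closed; the others are listed in step 4 of the working.
- A reader might take the word normally, used of treated patients in the Synopsis and section 5.1, as screening out atypical use. It may simply mean routine care, and the text shows no screening effect.

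**Conclusion.** The point holds in a limited form. Eligibility in 6.2.1 and the first Population row selects in part on the primary outcome, and it conflicts with 11.1 and the other Synopsis wordings. Where 6.2.1 is applied, the non-compliance rate can only be biased downwards, by q(1 − p) under full exclusion and by less if only some sites apply it.

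The size is conditional on q: nil at q = 0, and as large as the planned half-width once q reaches about 1.5% (p = 3%) to 2.0% (p = 5%). These figures assume full exclusion, that every vasoconstrictor-free use counts as non-compliant, and that the rates in section 11.4 can stand for p. The direction and the conflict in wording rest on the text alone. A later analysis plan could not repair the loss, because it cannot restore patients who were never documented.

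**What to change.** Use the unrestricted population of section 11.1 throughout:

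1. In 6.2.1, delete the parenthesis that requires a vasoconstrictor.
2. In the Synopsis, delete the first of the two Population rows.
3. In 11.2.1, state under the local anaesthetic point that a product without a catecholamine vasoconstrictor is classed as not complying. The anaesthetic product is already collected (section 8.1).

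The cost is a wording change in three places and possibly a small adjustment of the CRF. Section 8.1 has the inclusion criteria collected and the form uses tick boxes (section 9.2), but the form itself is not in the document, so this cannot be checked. The sample size and precision statement need no change. The reported compliance rate may turn out less favourable.
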